6	3.4.1.1 Delayed/Late Listeria Infection	21-22	Safety Section revised to include clinical experience to-date with Lm clearance and the description of the index case of delayed/late listeria infection.	Per FDA Safety Section, revised to inform investigators/patients on the recent delayed/late listeria event.
7	5.2 Exclusion Criteria (#14)	28	New exclusion criterion was added to exclude subjects with implanted devices that pose high risks for colonization or inability of removal.	Exclusion criteria added to mitigate risk of colonization of foreign bodies and medical devices
8	5.2 Exclusion Criteria(#15)	28	New exclusion criterion was added to exclude subjects who are receiving or are expected to receive treatment with PI3K or TNFα inhibitors during study participation or in future.	Exclusion criteria added to mitigate risk of listeria infection.

#	Section	Page	Revision	Rationale
9	5.2 Exclusion Criteria #16	28	New exclusion criterion was added to exclude subjects with a known contraindication (e.g. allergies/sensitivities) to the administration of trimethoprim sulfamethoxazole and/or ampicillin.	Exclusion criterion added based on FDA recommendation of prophylaxis and 6-month antibiotic treatment.
10	5.2 Exclusion Criteria (#21)	29	New exclusion criterion added to exclude subjects who have undergone a major surgery or had a newly implanted artificial (prosthetic) joint(s), implants and/or devices where a minimum of 6 weeks has not elapsed from the time of surgery. Additional requirements for the resolution of all toxicities and/or complications was included.	Exclusion criteria added as a required safety update to mitigate potential listeria events.
11	6 Study Design and Treatment Plan	29	Updated antibiotic regimen added.	Inclusion added based on FDA recommendation of antibiotic regimen for prophylaxis during study treatment and 6 month course post-treatment.
12	7.3 Patient Study Participation	33	New section added to detail patient study participation duration.	Updated to include the 3 year Lm Surveillance Monitoring Phase
13	Table 5: Schedule of Events	34-35	Added Lm Surveillance Monitoring schedule which includes a 6 month post ADXS11-001 antibiotic (Trimethoprim/Sulfamethoxazole) treatment to mitigate the risk of delayed listeria infection. Text clarified in the table footnotes for consistency with the revised corresponding study procedure.	Safety updates and administrative clarifications per FDA recommendation.
14	8.1 Study Procedures	36-38	Prior/Concomitant Therapies and Procedures and Adverse Events updated to require 6 month post-study treatment antibiotics as well as recording of adverse/serious events from the time informed consent is signed through the completion of Lm Surveillance period. Updated to require antibiotic usage to be documented on the respective eCRFs.	Safety updates and administrative clarifications per FDA recommendation.

#	Section	Page	Revision	Rationale
			Surgical History – surgical history will be obtained for all subjects. Surgical procedures that occur after study enrollment will be documented separately.	
			Prophylactic Medications – NSAIDS doses and antiemetic administration will be done per label or package insert.	
			Coagulation Profile – will be assessed at Screening only.	
			Dispense/Prescribe Oral Prophylactic Antibiotics section updated with details for on study and post study antibiotic regimen.	
15	8.5 Safety Follow- Up/Post-Treatment Visit	39-40	New paragraphs added regarding the updated Lm Surveillance Monitoring.	Safety update based on FDA recommendation.
16	9.1.1 Baseline Tumor Assessments	40	Section was updated by providing imaging areas to be included.	Safety administrative change
17	10.2.1 Safety Precautions	49	Section was updated to provide further clarification	Safety administrative change
18	11.1 ADXS11-001 Pretreatment Prophylaxis Regimen	51	Section was updated for revisions to the IV fluids volume and premedication regimen clarification	Safety administrative change
19	11.3 Administration of ADXS11-001	52	New paragraph added to note that	Safety update to mitigate potential listeria events.
20	11.5.1 and 11.5.2 Listeria Infection Identification and Management	57-59	New sections provide information on the identification process and management of potential/confirmed listeria infection.	Safety administrative change added to provide information on the identification and management of listeria.
21	11.7 Major and Minor Surgery and ADXS11-001 Treatment	61	New section added to describe the minimum time period required between major surgery and treatment administration for patients prior to and during study treatment.	Safety update to mitigate potential listeria events.

#	Section	Page	Revision	Rationale
22	12 Concurrent Therapies and Procedures	62-63	Added PI3K and TNFα to the list of prohibited therapies.	Safety update to include FDA recommendations.

1 SYNOPSIS

Sponsor:	Name of Finished Product:	Type of Treatment:
Advaxis, Inc.	ADXS11-001	Lm-LLO Immunotherapy

Study Title:

Phase 1 Study Evaluating High Dose ADXS11-001 Treatment In Women With Carcinoma of the Cervix

Type of Study:

Open-label, Phase 1

Study Centers: Multi-center

Objectives:

The primary objective of the study is:

- a) To evaluate the tolerability and safety of ADXS11-001 in subjects with persistent, metastatic, or recurrent squamous and non-squamous carcinoma, adenosquamous, or adenocarcinoma of the cervix Secondary objectives:
- a) To evaluate tumor response and progression-free survival (PFS) by Response Evaluation Criteria in Solid Tumors (RECIST) 1.1 and immune-related RECIST (irRECIST) criteria
- b) To evaluate and describe the data from correlative immunologic studies of ADXS11-001 treatment

Methodology:

In this Phase 1, dose-escalation, open-label, multi-center study, subjects with persistent, metastatic, or recurrent carcinoma of the cervix who have failed conventional therapy will receive ADXS11-001 every 3 weeks during a 12- week treatment cycle. Subjects will receive a prophylactic regimen to be completed at least prior to each ADXS11-001 infusion to mitigate and manage potential immune response seen with immunotherapy administration. In addition, all subjects will participate in a 3-year *Lm* surveillance period. The surveillance period will begin following the last dose of study treatment or at the time of study discontinuation. This period is intended to help ensure the eradication of *Lm* bacteria. This period will also include a 6-month course of trimethoprim/ sulfamethoxazole which will be initiated 72 hours at the completion of the last dose of ADXS11-001 or immediately following study discontinuation.

Doses will be escalated in the standard 3 + 3 fashion, starting with 5 x 10^9 colony forming units (CFU) to a maximum dose level of 1 x 10^{10} CFU. Dose cohorts of 3 subjects each will be treated. In the absence of dose-limiting toxicity (DLT) as defined in Section 6.1 Dose Limiting Toxicity assessed during the first treatment cycle, the dose will be escalated to the next dose level for the next 3 subjects. If DLT is seen in 1 of 3 subjects, another 3 subjects will be treated at that same dose. If DLT is seen in 2 of 6 subjects, then that dose level will be considered maximum tolerated dose (MTD) and the previous dose level will be selected as the recommended Phase 2 dose (RP2D). The RP2D will be selected based on an observed DLT rate of < 33%.

Treatment cycles can be repeated at the RP2D (or less) for an individual subject until a discontinuation criterion is met. Discontinuation criteria include documented disease progression, intolerable side effects not resolved with dose reduction or change in premedications or the subject completes 1 cycle of treatment post observation of complete response (CR) per RECIST 1.1 and immune-related RECIST criteria (irCR).

Sponsor:	Name of Finished Product:	Type of Treatment:
Advaxis, Inc.	ADXS11-001	Lm-LLO Immunotherapy

Further assessment of the RP2D level may be explored in an expansion cohort in subjects with persistent, metastatic, or recurrent carcinoma of the cervix who have failed conventional therapy to evaluate the safety and clinical activity of ADXS11-001. Treatment will continue for each subject until a discontinuation criterion is met. The end of treatment will be defined as 1 year after the last subject's first treatment or until that subject has met a discontinuation criterion. All subjects will be followed for adverse events (AEs) and serious adverse events (SAEs) from the time written informed consent is signed through the completion of the *Lm* surveillance period.

Safety will be assessed by comparing treatment-related AEs, changes in physical examinations, vital sign measurements, laboratory abnormalities and *Lm* surveillance monitoring.

Immunologic effects will be measured and evaluated by collection of peripheral blood for preparation of peripheral blood mononuclear cells (PBMCs) and serum in cycle 1 only. PBMCs will be analyzed for the presence and quantitation of HPV-E7 and HPV-E6 specific CD8+ T-cells through ELISpot and other assays as well as T regulatory cells and myeloid-derived suppressor cells. PBMC immunologic gene expression analysis may also be conducted. Serum will be evaluated for serum cytokines, chemokines, and other potential markers.

Number of Subjects Planned:

The dose escalation portion of the study will enroll between 6-12 subjects based on observed AEs and/or DLTs within the dose cohorts. Additional subjects may be enrolled in an expansion cohort at the RP2D level to allow approximately 15 subjects to be treated at that dose level.

Diagnosis and Main Criteria for Eligibility:

- Women at least 18 years of age with histologically-confirmed, measurable and/or evaluable disease as defined by RECIST 1.1
- Subject has persistent, metastatic, or recurrent squamous and non-squamous carcinoma, adenosquamous, or adenocarcinoma of the cervix with documented disease progression that is not amenable to surgery or standard radiotherapy
- Subject may have received ≤2 prior regimens for disease in the metastatic setting. Subjects who have had >2 prior therapies in the metastatic setting MAY be eligible only after consultation with the Investigator and the Sponsor.
- Subjects should have no major existing co-morbidities or medical conditions that will preclude therapy in the view of the principal investigator
- Subjects must have an Eastern Cooperative Oncology Group (ECOG) performance status of 0 or 1, and a life expectancy of at least 6 months (to be able to complete 1 study cycle)
- Subjects should not have rapidly progressing disease
- Subjects must be able to tolerate trimethoprim/sulfamethoxazole and ampicillin.
- Subjects must not have implanted medical device(s) that pose a high risk for colonization
 and/or cannot be easily removed (e.g., prosthetic joints, artificial heart valves, pacemakers,
 orthopedic screw(s), metal plate(s), bone graft(s), or other exogenous implant(s)). More
 common devices and prosthetics such as: arterial and venous stents, dental and breast implants
 and venous access devices such as Mediports are permitted. Subjects with any other devices or
 implants must be approved by Sponsor prior to participation.

Sponsor:	Name of Finished Product:	Type of Treatment:
Advaxis, Inc.	ADXS11-001	Lm-LLO Immunotherapy

- Subjects who have undergone a major surgery or who have a new artificial implant and/or medical device which meets eligibility criteria must have a minimum 6-week time period elapsed from the time of surgery to the initiation of study treatment.
- Subjects who are receiving or are expected to receive future treatment with PI3K or TNFα inhibitors.

Test Product, Dose, Mode of Administration:

ADXS11-001 is a live attenuated bioengineered strain of Listeria monocytogenes (Lm)-LLO.

Reference Therapy:

None

Study Duration:

Each subject will participate in the trial for up to 5 years from the time the subject signs informed consent through the final study contact. The study duration includes an active study treatment phase (~24 months) and a 3-year *Lm* surveillance monitoring period, which includes 6 months of oral antibiotic administration to commence upon completion of the active study treatment phase or upon study discontinuation.

Criteria for Evaluation:

Safety: Recorded AEs; physical examinations, including vital sign measurements; clinical laboratory evaluations; *Lm* surveillance blood cultures

Efficacy: Tumor response and progression free survival (PFS)

Immunologic effects: Collection and analysis of peripheral blood

Statistical Methods:

Descriptive statistics will be used to summarize and evaluate the outcomes.

Demographic and baseline subject characteristics will be summarized. AEs will be classified and summarized by type, incidence, severity, and causality. All AEs will be summarized by subject, dose level, and prior recurrence history (aggressive/non-aggressive). All subjects who received at least 1 dose of ADXS11-001 will be included in the safety analyses.

Disease response will be tabulated for all subjects who receive ADXS11-001. PFS is defined as the time from first dose of study treatment until objective tumor progression or death. Subjects who have not progressed or who are still alive at the time of evaluation will be censored for the analysis. Kaplan-Meier curves and descriptive statistics will be used to summarize PFS.

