11.8 Discontinuation of Study Subjects

11.8.1 Subject Study Discontinuation Criteria

Subjects may withdraw consent at any time for any reason or be discontinued from the trial at the discretion of the investigator, should any untoward effect occur. In addition, a subject may be withdrawn by the investigator or the sponsor if enrollment into the trial is inappropriate, the trial plan is violated, or for administrative and/or other safety reasons.

A subject may be discontinued from the trial for any of the following reasons:

- Screen Failure
- AE/SAE
- Lost to Follow-Up
- Disease Progression
- Death
- Withdrawal of Consent by Subject
- Investigator Decision/Study Non-Compliance by Subject
- Achieved Complete Remission
- Completed Study (at least 24 months of study treatment)
- Other (specify)

In all cases, the reason for and date of withdrawal must be recorded in the eCRF and in the subject's medical records. The subject must be followed up to establish whether the reason was an AE, and, if so, this must be reported.

When a subject discontinues/withdraws prior to study completion, all applicable activities scheduled for the final assessment (End of Therapy assessments) should be performed at the time of discontinuation. Any AEs that are present at the time of discontinuation/withdrawal should be followed in accordance with the safety requirements outlined in Section 13.2 Collection of Safety Information.

The Investigator must make every effort to contact subjects who discontinue the study prematurely or are lost to follow-up and to schedule the end of therapy assessments. Attempts to contact such subjects must be documented in the subject's records (e.g., times and dates of attempted telephone contact, receipt for sending a registered letter).

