14.5.5 Analysis of Efficacy

All subjects who complete at least one cycle of ADXS11-001 treatment will be included in the efficacy analyses. The following are efficacy parameters for the study:

- 1. Objective Response Rate (ORR)
- 2. Duration of tumor response
- 3. Stable Disease Rate (proportion of CR, PR, SD)
- 4. Duration of Stable Disease (SD)
- 5. Progression free survival (PFS)

Tumor response will be evaluated by RECIST 1.1 and irRECIST criteria. The ORR will be calculated as the proportion of subjects who achieved CR/irCR or PR/irPR. The duration of response is defined as the time interval from CR/irCR or PR/irPR to disease progression or death. If the subject's disease remains responsive by the time of discontinuation or completion of the study, the duration will be censored at that time point. The stable disease rate will be calculated as the proportion of subjects who achieved CR/irCR, PR/irPR or SD/irSD. The duration of SD is defined as the time interval from CR/irCR or PR/irPR or SD/irSD to disease progression or death. If the subject's disease remains stable by the time of discontinuation or completion of the study, the duration will be censored at that time point.

PFS is defined as the time interval from first infusion of study treatment to disease progression or death. If the subject's disease has not progressed by the time of discontinuation or completion of the study, the PFS will be censored at that time point.

Efficacy parameters will be descriptively summarized by dose cohorts as well as for all cohorts combined. Tumor response will be summarized according to response category. Response rate and stable disease rate will be summarized by frequency table. For durations of response and SD/irSD as well as PFS, the Kaplan-Meier method will be used to estimate the median times. Descriptive statistics and Kaplan-Meier curves will be presented.

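### The Synopsis PFS censoring sentence contradicts the PFS definition beside it and Section 14.5.5; Section 14.5.5 itself leaves deaths without documented progression open to censoring

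*Combined protocol and SAP*

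**What the plan says.** **Event definition.** The two places agree. Synopsis, Statistical Methods: "PFS is defined as the time from first dose of study treatment until objective tumor progression or death". Section 14.5.5: "PFS is defined as the time interval from first infusion of study treatment to disease progression or death".

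**Censoring rule.** The two places differ.
- Synopsis: "Subjects who have not progressed or who are still alive at the time of evaluation will be censored for the analysis".
- Section 14.5.5: "If the subject's disease has not progressed by the time of discontinuation or completion of the study, the PFS will be censored".

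**Related durations.** Section 14.5.5 defines duration of response and duration of stable disease as ending at progression or death, then uses the same kind of censoring sentence. For response: "If the subject's disease remains responsive by the time of discontinuation or completion of the study, the duration will be censored at that time point". Its counterpart for stable disease has the same structure.

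**Discontinuation.** Section 11.8.1 opens a list with "A subject may be discontinued from the trial for any of the following reasons", and Death is one of the entries.

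**Summary measure and population.** "For durations of response and SD/irSD as well as PFS, the Kaplan-Meier method will be used to estimate the median times". Sections 14.5 and 14.5.5 limit the efficacy analyses to subjects who complete at least one cycle. No other part of Section 14 gives a PFS censoring rule.

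**The concern.** A time-to-event analysis needs every subject to be either an event or censored, and the two rules must fit together. Here the Synopsis definition makes a living progressor an event, while the next sentence censors her. The Synopsis also disagrees with Section 14.5.5 about the same subject, so a programmer cannot follow both. In Section 14.5.5, a subject who dies without a progression scan meets the definition of an event. She can also be read as not having progressed by discontinuation, because death is a listed discontinuation reason.

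Both kinds of record will occur. Imaging is every 12 weeks, so deaths between scans are possible. Progression ends treatment and subjects then enter a 3-year surveillance period, so living progressors will be common. PFS is a named secondary objective, about 15 subjects are planned at the recommended dose, and results are reported by dose cohort. A few misclassified records would be visible, and they would shift the result in the product's favour.

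**Working it through.** The documents give no PFS median or event count, so there is no figure to reproduce.

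**Step 1. Classify the four possible states under each text, read literally.**

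| Progressed | Died | Definition (both places) | Synopsis sentence | 14.5.5 sentence |
|---|---|---|---|---|
| No | No | censored | censored | censored |
| No | Yes | event | censored | censored (if death counts as discontinuation) |
| Yes | No | event | censored | event |
| Yes | Yes | event | event | event |

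The definition yields events in three states, the Synopsis sentence in one and the 14.5.5 sentence in two. A rule that censors only subjects alive and without progression matches the definition in all four.

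**Step 2. Direction.** Turning an event into a censored record at the same time removes a factor below 1 from the Kaplan-Meier product. Moving the censoring later also enlarges the intervening risk sets. Either way the curve, and so the median, can rise or stay the same but cannot fall. This needs no assumption.

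**Step 3. Size, under assumptions that are not in the documents.** Exponential times; true median PFS 3 months, so h = ln 2 / 3 = 0.231 per month; a share q = 0.10 to 0.20 of first events are deaths without progression; median survival after progression 6 to 8 months, with hazard g = ln 2 / 6 to ln 2 / 8; the same follow-up F for everyone; all treated subjects.

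*14.5.5 sentence.* Deaths without progression are censored, so the counted hazard is (1 − q)h and the median is 3 / (1 − q). This is 3 / 0.9 = 3.3 months for q = 0.10 and 3 / 0.8 = 3.75, about 3.8 months, for q = 0.20.

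*Synopsis sentence, living progressors censored at progression.* A progression at time t counts only if death follows before F. The counted hazard is (1 − q)h[1 − exp(−g(F − t))], and the median t solves

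(1 − q)h · {t − [exp(−g(F − t)) − exp(−gF)] / g} = ln 2.

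For F = 12, q = 0.10 and 6 months of post-progression survival, g = 0.1155. At t = 5.05 the left side is 0.9 × 0.231 × [5.05 − (0.448 − 0.250) / 0.1155] = 0.9 × 0.231 × 3.335 = 0.693, so the median is about 5.0 months.

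*Synopsis sentence, living progressors censored at evaluation.* Obtained by simulation under the same assumptions.

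Medians in months (true value 3.0):

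| Follow-up | 14.5.5 | Synopsis, censored at progression | Synopsis, censored at evaluation |
|---|---|---|---|
| 12 months | 3.3–3.8 | 5.0–7.5 | 7.2 to not reached |
| 24 months | 3.3–3.8 | 3.6–4.4 | 3.8–4.8 |
| 36 months | 3.3–3.8 | 3.4–4.0 | 3.4–4.1 |

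Expected events among 15 subjects at 12 months: 14.1 by the definition, 11.2 to 12.7 under 14.5.5, and 5.7 to 7.6 under the Synopsis.

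**Step 4. The one-cycle population.** If deaths without progression before week 12 are left out, as Section 14.5.5 implies, the 14.5.5 effect falls to about 2% to 5%: 3.2 to 3.3 months for q = 0.10 and 3.4 to 3.6 for q = 0.20.

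**Step 5. Other assumptions.** With a true median of 4.0 months, q = 0.10, 6 months of post-progression survival and evaluation 12 to 24 months after first dose, the 14.5.5 sentence gives 4.4 months. The Synopsis sentence gives 5.5 months (censored at progression) or 6.1 months (censored at evaluation). The direction is the same.

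**The case against.** The strongest reply is that this is a drafting slip. Each censoring sentence follows directly after a definition that names progression or death, and an analyst who works from the definition gets the right answer. Counting only subjects who progressed and then died is not PFS on any reading. This stands as a limit on the consequence: inflation arises only if the sentences are programmed as written. It does not remove the contradiction, and nothing else in Section 14 settles it.

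The reply is stronger for Section 14.5.5. Its interval ends at death, so a subject who died has reached an endpoint and there is nothing left to censor. The contrary reading takes Death from a disposition list that is not an analysis rule. That limb is therefore an ambiguity, not a clear error.

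Four stronger readings are tempting but unsupported.
- A reader might infer that both texts censor living progressors. Only the Synopsis does.
- A reader might infer that most early events are lost. Under the assumptions above, living progressors make up 23% to 36% of the events occurring by month 3 with 12 months of follow-up, and 6% to 13% with 24 months. Early progressors have had the longest time to die.
- A reader might take a death at month 2 as a record censored under Section 14.5.5. That subject has not completed a 12-week cycle and is excluded from the efficacy population. A death at month 5 without a progression scan would show the defect.
- A reader might take the 12-month medians as the expected size. The Synopsis counts its one-year limit from when the last subject starts treatment, so earlier subjects have longer follow-up. Deaths are reportable through the 3-year surveillance period (Section 13.7.1). With longer follow-up the Synopsis effect shrinks towards that of Section 14.5.5.

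**Conclusion.** The Synopsis sentence is wrong as written: it contradicts its own definition and conflicts with Section 14.5.5 over living progressors. Section 14.5.5 is incomplete on deaths without documented progression after cycle 1, for PFS and for the durations of response and stable disease.

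The direction of any error is certain, but its size is not. Every input to the medians is assumed, and the simulation ignores the 12-weekly imaging grid, which is coarser than the 0.3 to 0.8 month shift under the 14.5.5 sentence. The documents do not support saying that the reported median will be inflated, only that it can be if either sentence is followed literally.

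PFS is a secondary, descriptive endpoint. No test or sample size rests on it, and the recommended dose is chosen on dose-limiting toxicities. The wording should still be corrected, because the endpoint is a named objective and the correction is nearly free.

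**What to change.** Put one rule in both the Synopsis and Section 14.5.5:

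*Only subjects who are alive and without progression are censored; death from any cause without prior progression is an event at the date of death.*

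Apply the same rule to duration of response and duration of stable disease, so that a death during response or stable disease ends the interval as an event.

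The cost is two or three sentences of wording and no new data. The resulting median will be equal to or lower than the one the literal sentences would give.
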